## Summary

This protocol details the phase IV study aiming to assess both impact and implementation of a new clinical prediction rule (CPR) only based on patient's history and physical examination in order to help general practitioners ruling out a cardiac origin to chest pain without further investigations. It is built upon the data of the TOPIC (Thoracic Pain In Community) study run in 2001 to measure occurrence and aetiologies of chest pain in primary care. Internal and external validation studies have been done by now. The current study is a prospective cohort cluster randomized trial with two arms: on one hand general practitioners aided by the CPR and on the other hand general practitioners working according to their usual clinical practice. The target population is patients consulting primary care settings and reporting any type of chest pain. We will measure the acceptability, satisfaction and use of the CPR by physicians and intend to show that it can spare useless extra investigations without compromising patients' management and outcome. To reach this goal, 300 general practitioners and 15,000 patients are needed. Inclusion and exclusion criteria are defined. The follow-up lasts 9 months and the main endpoints measured are hospitalizations, diagnostic of coronary artery disease, extra investigations and referrals run to determine the origin of chest pain. We will also assess use, acceptability of the CPR and satisfaction among the physicians selected to use it. An intermediate analysis is planned at 3 months and stopping rules are defined. A case report form has to be filled in for each patient with chest pain. No adverse events are expected. Independent reviewing and follow-up will insure correct management of the patients enrolled. The current protocol will be submitted to an ethical committee.

## Synopsis

Study subject	Clinical prediction rule to help general practitioners rule out a serious cardiac condition in primary care patients complaining of chest pain.
Study title	Implementation study of a clinical prediction score to rule out cardiogenic chest pain in community: cluster randomized trial.
Investigators	Principal investigator : to be defined Investigators : to be defined
Study centre	Institute for General Medicine, University of Lausanne, Switzerland
Study place	Western Switzerland private primary care settings ; Department of Ambulatory Care and Community Medicine, University of Lausanne
Study period	To be defined
Objectives	
 
1. To measure the acceptability, satisfaction and use of the clinical prediction rule by general practitioners in primary care patients complaining of chest pain.
 
2. To show that using the cardiovascular clinical prediction rule as an assistive tool to rule out coronary heart disease in primary care practice can spare useless extra investigations, without compromising patient's management and outcome.
 

Methodology	Prospective cohort cluster randomized trial
Number of patients	15,000 patients
Number of physicians	300 physicians
Selection criteria	
Inclusion criteria: patients aged 18 years and over reporting any type of chest pain, even if chest pain is not the main complaint, if it is revealed by systematic anamnesis or if there is yet a known history of chest pain or cardiovascular disease.
 
Exclusion criteria: patients unable to communicate with physicians, for whom follow-up may not be feasible, obvious traumatic or extrathoracic origin to chest pain, psychiatric severe comorbidities, refusal or impossibility to consent.

Duration	At most 9 months follow up per patient
Reference	Usual primary care practice
Evaluation	
 
- Hospitalizations, severe CHD at 9 months
 
- Number and type of extra investigations and referrals
 
- Use/non use of the CPR, acceptability and satisfaction
 

Statistical method	STATA (data analysis and statistical software)

## **Abbreviations**

CHD	Coronary Heart Disease
CPR	Clinical Prediction Rule
CRF	Case Report Form
GP	General Practitioner

## 1. Background

### 1.1 Fundamentals

Chest pain is a common complaint in primary care patients (1 to 3% of all consultations) (1) and its aetiology can be miscellaneous, from harmless to potentially life threatening conditions. In primary care practice, the most prevalent aetiologies are: chest wall syndrome (43%), coronary heart disease (12%) and anxiety (7%) (2). In up to 20% of cases, potentially serious conditions as cardiac, respiratory or neoplastic diseases underlie chest pain. In this context, a large number of laboratory tests are run (42%) and over 16% of patients are referred to a specialist or hospitalized (2).

A cardiovascular origin to chest pain can threaten patient's life and investigations run to exclude a serious condition can be expensive and involve a large number of exams or referral to specialist - often without real clinical need. In emergency settings, up to 80% of chest pains in patients are due to cardiovascular events (3) and scoring methods have been developed to identify conditions such as coronary heart disease (CHD) quickly and efficiently (4-6). In primary care, a cardiovascular origin is present in only about 12% of patients with chest pain (2) and general practitioners (GPs) need to exclude as safely as possible a potential serious condition underlying chest pain. A simple clinical prediction rule (CPR) like those available in emergency settings may therefore help GPs and spare time and extra investigations in ruling out CHD in primary care patients. Such a tool may also help GPs reassure patients with more common origin to chest pain.

### 1.2 Study clinical prediction rule

In order to help GPs rule out a serious cardiac condition in patients complaining of chest pain, several CPRs have been developed in the last few years, two of them in Switzerland (7, 8) and Germany (9, 10). They are only based on patient's history and physical examination and aim to define the risk of cardiac origin to chest pain.

The Swiss CPR allows points to each of the seven following items: known cardiovascular risk, men over 55 years or women over 65 years, personal history of cardiovascular disease, substernal pain (two points each), duration of pain from 1 to 60 minutes, increasing with effort, absence of tenderness at palpation (one point each). Cut-off point for the low-risk group is 5. This rule showed a sensitivity of 97.6% and a specificity of 71.3% in ruling out CHD, a negative likelihood ratio of 0.033 and a negative predictive value of 99.5% in the derivation cohort. External validation has been done using the cross-country cohorts and showed a sensitivity of 85.6% a specificity of 47.2%, a negative predictive value of 94.8% and a negative likelihood ratio of 0.305 for the Swiss CPR (N.B.: inclusion criteria in both German and Swiss studies were not the same, which may explain at least part of the difference between results of internal and external validation studies) (8).

German investigators have also run a further external validation study with a new cohort that confirms the validity of their CPR. The Marburg Heart Score showed a sensitivity of 89.1%, a specificity of 63.5%, a positive predictive value of 23.3%, a negative predictive value of 97.9%, a positive likelihood ratio of 2.44 and a negative likelihood ratio of 0.17. Germans also noticed that GPs whose clinical judgment was aided by the score showed a higher sensitivity (90.0 versus 82.9%) and specificity (66.8 versus 61.8) than those working without the score, but the difference was not

[figure not shown]
significant (11). More results should soon confirm safety and robustness of such CPRs, especially the final results and publication of the Marburg Heart Score.

Both CPRs aim to define low-risk patients and rule out CHD without further investigations. We strongly believe that using such CPRs may improve the management of chest pain in primary care in the same way the D-dimers test does in ruling out venous thromboembolism without computer tomography or ultrasound (since it has high sensitivity and negative predictive value). Moreover, it may reduce extra investigations and costs for patients of equivalent risk of cardiogenic chest pain.

We however remember that such CPRs are not valid for patients with chest pain in emergency settings or at the cardiologist office, as there are already scoring methods and diagnostic tools available and validated to rule out CHD in those structures. Besides, the prevalence of diseases is not the same in primary care (low prevalent setting) than in more specialized settings (**Figure A**). Specialists and hospitals usually get a minor part of general population, as patients have often already been selected in primary care settings, while GPs have to deal with the whole population - with early, untypical and unselected symptoms - and its own repartition of diseases. It is therefore worth having an assistive tool such as a CPR especially developed for general practice and its own needs.

We are now waiting for the last results from the international collaborating studies, confirming validity of those CPRs for primary care practice. Next step is to run an implementation study to show that the cardiovascular CPR can be applied and is effective as an assistive prediction tool for GPs. The current protocol describes the phase IV study aiming to measure use of such a CPR among GPs and its impact on everyday primary care practice (extra-investigations, referrals, patients outcome).

**Figure A:** Comparison between chest pain aetiologies in primary care (TOPIC study) and in emergency settings

[figure not shown]
### 1.3 Study rationale

The study is a phase IV study and will take place in Swiss primary care settings. Target population are patients over 18 years consulting GPs and reporting any type of chest pain. We built a two arms trial to compare management of chest pain either in usual practice or aided by the cardiovascular CPR.

We chose a cluster randomized trial design and the intervention will be performed at the level of GP's offices. Randomization within the same health care unit and intervention performed at patient's level would have led to an important selection bias. This would have made impossible to guarantee an equivalent management of patients within the same arm as well as a strict distinction between the two arms.

GPs will therefore be enrolled in a prospective study and randomized either to use the Swiss CPR as an additional tool for the management of chest pain or go on with their usual practice. Each GP will have to include a defined number of patients complaining of chest pain.

Follow-up will concern number and type of paraclinical tests run by GPs, referrals and patient's outcome. We will also appreciate the use of the CPR, its acceptability and the satisfaction among the selected GPs. An intermediate analysis is planned during follow-up and stopping rules are defined in case of necessity.

## 2. Objectives

- To measure the acceptability, satisfaction and use of the CPR by GPs in primary care patients complaining of chest pain.
- To show that using the cardiovascular CPR as an assistive tool to rule out CHD in primary care practices can spare useless extra investigations, without compromising patient's management and outcome.

## 3. Study design

[figure not shown]
### 3.1 Overall description

This trial aims to assess implementation of a new cardiovascular CPR in primary health care. It is built as a prospective cohort study of primary care patients with chest pain. The cluster randomized trial design allows us to randomize GP's offices in two groups, one using the CPR in daily practice and the other working without, according to usual care practice. Thus, randomization and intervention are targeted at the level of GP's offices. Patient's outcome however is measured at the individual's level thanks to a case report form (CRF). Use of the CPR is measured directly by a few questions intended for GPs.

GPs selected to use the cardiovascular CPR will get intensive training to make as sure as possible that they use it in an equivalent way (see Annex 1 for description of GPs training). GPs of the usual practice group should not be aware of the CPR and will not get any information about it. In both groups, GPs will have to fill in a CRF for each patient complaining of chest pain.

Follow-up ends nine months after patient's index visit. An intermediate analysis is planned at three months. Members of research staff are designed to make sure that case report forms are complete for each patient and will get in touch with every agreeing patient at three months (intermediate analysis). GPs will assure the follow up until nine months (end of follow up) either by telephonic interviews or usual consultation. The research staff will control the follow up and remember GPs if necessary.

Independent physicians will review a defined randomized number of cases. They will control patient's condition at the end of the follow-up, validate the correct management of patients and verify the validity of the initial diagnosis of cardiogenic chest pain.

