### 3.5 Data collected in the CRF

A case report form (CRF) has to be filled in by all the GPs for each patient included to define patient's characteristics, current pain, personal history of cardiovascular disease and risk factors. It will also provide investigators with information regarding complementary investigations, referrals or hospitalizations for each patient at the time of index visit.

GPs of the intervention group will be asked to calculate the risk of cardiogenic chest pain for each patient with the CPR. The CRF also includes questions directly addressed to GPs to appreciate use, satisfaction and acceptability of the CPR.

GPs who belong to the usual care group will have to evaluate the risk of cardiogenic chest pain according to their clinical judgement only.

As all the items of the CPR are part of usual practice (patient's history and physical examination) investigators will be able to calculate patients' risk of cardiogenic chest pain a posteriori in the usual care group with the data collected in the CRF.

[figure not shown]
(See Annex 2 for complete CRF)

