### Douleur thoracique:

**Contexte :** nouvelle  / connue  plainte principale  / plainte secondaire

**Intensité:** faible  modérée  forte

[figure not shown]
**Installation:** soudaine  progressive

**Evolution:** en augmentation  en diminution  intermittente   
constante avec exacerbations

**Durée:** <1 minute  <15 minutes  <1 heure  heures   
jours  mal défini

**Type:** superficielle  profonde  oppressante  en lancées   
brûlure

**Localisation :** rétrosternale  transfixiante  localisée  étendue

Préciser (avec irradiation si présente) :

**Facteur déclenchant:** effort  mouvement  décubitus  repas   
anxiété  palpation

**Facteur aggravant:** toux  respiration  position  déglutition   
effort

Autre(s) caractéristique(s) (préciser) : \_\_\_\_\_

**Symptômes d'accompagnement :****Général :** fièvre  frissons  sudations  altération conscience **Cardiovasculaire :** palpitation  syncope  tachycardie  arythmie   
instabilité hémodynamique   
autre  (préciser) : \_\_\_\_\_**Respiratoire :** dyspnée  toux  expectorations   
autre  (préciser) : \_\_\_\_\_**Digestif :** dysphagie  reflux  épigastralgies   
autre  (préciser) : \_\_\_\_\_**Articulaire :** préciser si présent(s) : \_\_\_\_\_**Facteurs de risque :**HTA  diabète  dyslipidémie Tabagisme  : \_\_\_\_ UPA OH  : \_\_\_\_ dl/semaineAnamnèse familiale positive Antécédents personnels cardiovasculaires (maladie coronarienne, maladie cérébrovasculaire, artériopathie périphérique) Antécédent personnel maladie thromboembolique veineuse **Score clinique cardiovasculaire (uniquement pour les médecins du « groupe CPR ») :**

Swiss Heart Score	
Men over 55 years, women over 65 years	2 points
Known cardiovascular risk	2 points
Personal history of cardiovascular disease	2 points
Substernal pain	2 points
Duration of pain from 1 to 60 minutes	1 point
Increasing with effort	1 point
No tenderness at palpation	1 point
Total < 5 points: low risk of cardiogenic chest pain	
Total 5 to 7 points: intermediate risk of cardiogenic chest pain	
Total > 7 points: high risk of cardiogenic chest pai	
- Sensitivity 97.6%, specificity 71.3%, negative likelihood ratio 0.033, negative predictive value 99,5% (derivation cohort)	
- Sensitivity 85.6%, specificity 47.2%, negative likelihood ratio 0.305, negative predictive value 94.8% (validation cohort)	

**Total :** \_\_\_\_ points

Alternativement :

Marburg Heart Score	
Men over 55 years, women over 65 years	1 point
Known clinical vascular disease*	1 point

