**Appréciation du score clinique cardiovasculaire (uniquement pour les médecins du « groupe CPR ») :**

Utilisation *au cours* de la consultation :      oui  / non

*Sinon, pourquoi ?* Oubli       inadapté       autre  (préciser) : \_\_\_\_\_

Si le résultat du score a indiqué un *risque faible* d'origine cardiaque à la douleur thoracique :

Aucun impact      0 - 1 - 2 - 3 - 4      Rassurant

Degré de satisfaction : insatisfaisant      0 - 1 - 2 - 3 - 4      très satisfaisant

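### The only index-visit CRF in the protocol prints the full score, although control GPs are to get no information about it, and no control-arm version is described

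*Protocol*

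**What the plan says.** Section 3.1 of the protocol sets the separation of the arms: "GPs of the usual practice group should not be aware of the CPR and will not get any information about it". The next sentence reads: "In both groups, GPs will have to fill in a CRF for each patient complaining of chest pain". Section 3.5 repeats this ("A case report form (CRF) has to be filled in by all the GPs for each patient included"), adds that "The CRF also includes questions directly addressed to GPs to appreciate use, satisfaction and acceptability of the CPR", and closes with the pointer "See Annex 2 for complete CRF".

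Annex 2 holds one index-visit form. After the risk-factor items comes a block headed "Score clinique cardiovasculaire (uniquement pour les médecins du « groupe CPR". It contains the seven Swiss Heart Score items with their points, the low, intermediate and high bands, and the sensitivity, specificity, negative likelihood ratio and negative predictive value from both the derivation and the validation cohort. The Marburg Heart Score follows as an alternative, also with points, cut-off and accuracy. Below these come the fields for diagnostic impression, tests done at the visit and onward management. The form ends with a second block, "Appréciation du score clinique cardiovasculaire", on use of the score, reassurance and satisfaction; its heading carries the same restriction to CPR-group doctors.

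The list of appendices names one case report form. The script for the usual-care GPs in Annex 1 does not mention the CPR.

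**The concern.** Section 1.3 justifies cluster randomisation by the need to keep the two arms strictly distinct. A form that carries the rule into control practices works against that purpose. A control GP who reads the block can apply the score, because its items are ordinary history and examination findings and most of them are recorded on the same form.

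If some control GPs act on what they read, the rates of tests and referrals in the two arms move closer together. That makes a real reduction in investigations harder to show. It would also make an absence of difference in patient outcome look more reassuring than it should. The comparison of low-risk patients between arms in section 10.2(e) would be diluted in the same way. Section 3.4 lists lack of a significant difference among the stopping rules at the 3-month analysis, so dilution could also affect the decision to continue.

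**Working it through.** **Reading the passages together**

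1. Who must not learn of the rule: control GPs (section 3.1).
2. Who completes the CRF: GPs in both groups (sections 3.1 and 3.5).
3. Which CRF: Annex 2, the only index-visit form in the protocol and the one that section 3.5 calls complete.
4. What it shows: the whole rule, twice over (Swiss and Marburg), and the appraisal questions.
5. What separates the arms on paper: the words "uniquement pour les médecins du" followed by the name of the CPR group. This tells a control GP not to complete the block. It does not remove the block, and it reveals that a score and a CPR group exist.
6. Whether a control version is described anywhere: no.

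Steps 1 to 4 cannot all be honoured with the form as annexed.

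**Scale of exposure**

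Section 10.1 plans 150 GPs per arm with 50 patients each. That is up to 50 index forms per control GP and 150 × 50 = 7,500 control-arm forms. The score block stands above the fields for tests. Even if a GP fills in the first form only after the consultation, the rule has been seen before the next patient.

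**Illustration of the possible loss of power**

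The plan's own calculation cannot be reproduced: its table is among the figures not shown, and the readable text gives neither the intervention-arm proportion nor alpha and power.

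- From section 10.1: control proportion p0 = 0.42 (284/672, rounded), m = 50 patients per GP, coefficient of variation k = 0.2, c = 150 GPs per arm.
- Assumed: intervention proportion p1 = 0.38, two-sided alpha 0.05, and a fraction q of the effect reaching the control arm.

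Standard formula for an unmatched cluster trial with proportions:

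V = p0(1 − p0)/m + p1(1 − p1)/m + k²(p0² + p1²)

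V = 0.2436/50 + 0.2356/50 + 0.04 × (0.1764 + 0.1444) = 0.004872 + 0.004712 + 0.012832 = 0.022416

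SE = √(V/(c − 1)) = √(0.022416/149) = 0.01227

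z = 0.04/0.01227 = 3.26

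Power = Φ(3.26(1 − q) − 1.96)

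| q | Difference left (points) | Power |
|---|---|---|
| 0 | 4.0 | 90% |
| 10% | 3.6 | 84% |
| 20% | 3.2 | 74% |
| 30% | 2.8 | 63% |

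The table holds SE fixed. Recomputing it as the control rate falls changes these powers by less than one percentage point.

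The starting point matters. If 150 GPs per arm instead corresponded to 80% power (42.3% versus 38.8% by the same formula), leakage of 10%, 20% or 30% would give about 72%, 62% or 51%. No value of q can be taken from the documents.

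**The case against.** The strongest reply is that Annex 2 is a master template and not the form to be printed. It shows both scores as alternatives, while section 5 says that one will be chosen before submission to the ethics committee, so this exact page is probably not meant for either arm. The CPR-only headings could mark content to be left out for controls. The statement in section 3.1 that controls get no information could itself be read as governing what is printed for them. Controls have no need of the block, since section 3.5 has the investigators calculate their scores afterwards from the raw items.

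This is a plausible account of the intention, and it limits what can be claimed. It does not settle the matter, because nowhere does the protocol say that the blocks are removed for controls. A team that followed it literally would hand out Annex 2 to everyone.

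A reader might also infer stronger conclusions that the documents do not support:

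- **That the intervention is delivered to the control arm.** The intervention is personal training plus the instruction to calculate the score before deciding on tests. A box marked as not for the reader is exposure, not delivery.
- **That section 3.5 is contradicted where it restricts controls to clinical judgement.** A control GP who respects the heading still complies. The conflict is with the sentence in section 3.1.
- **That a null result could not be told apart from contamination.** Even at 30% leakage the illustration leaves a 2.8-point difference.
- **That the power figures measure a loss in this trial.** The 38%, the alpha and the leakage fractions are all assumed, and the formula credits an influenced but untrained control visit with the full effect of training and scoring.

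**Conclusion.** The concern holds as an inconsistency between section 3.1 and the annexed form. Control GPs are to know nothing of the rule, yet the only CRF that the protocol gives them prints all of it, under a heading that does not conceal it. Used as annexed, the form would expose the control arm and could bias the comparison towards no difference.

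That exposure would follow from using this form is clear from the text. How far it would change control GPs' behaviour is unknown. The fall from about 90% power to between 84% and 63% shows only that modest leakage would matter at the planned size. The finding does not depend on it. The point should be settled before enrolment, because exposure cannot be undone afterwards.

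**What to change.** State in sections 3.1 and 3.5 that the CRF exists in two arm-specific versions, and annex both. The usual-care version should omit the score block, the appraisal block and any mention of a *groupe CPR*. Keep the raw clinical items identical in both versions, so that the score can still be calculated afterwards for control patients as section 3.5 requires. The CPR version should carry only the score finally chosen, which section 5 already implies.

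The cost is one extra form version and its version control.

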### 7.2 Documents storage and keeping

The documents collected during the current study are the CRF, questionnaires filled in by research team at 3 months and end of follow up questionnaires for each patient included. All the files regarding the current trial will be kept at the Institute of General Medicine, University of Lausanne, Switzerland.

GPs have to send index visit CRF to research team once a week, as well as end of follow up questionnaires (routine consultation 6 to 9 months after index visit or telephonic interview). Questionnaires for intermediate analysis at 3 months will be filled in by research team during a telephonic interview and kept in the research department.

A single code will be attributed to each patient and GP, so that complete anonymity is insured. Patients' details will be known only by their GP to insure maximal confidentiality. Each GP makes a ranking list of participating patients with name, code and phone number to assure the follow up. Furthermore, and only with patients' consent, mobile phone number is attached to identification code to allow the research team to contact patient in case of incomplete CRF. Mobile phone numbers will be deleted after intermediate analysis.

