### **8.2 Monitoring of adverse events**

Intermediate analysis is done at 3 months after patients index visit to display any unexpected effect of the CPR. In case of unfavourable effect for patients included, study will be immediately stopped. For stopping rules, please refer to *Chapter 3.4*.

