## **9. Quality control and assurance**

### **9.1 Monitoring**

Follow-up will last 6 to 9 months, with intermediate analysis at 3 months. To insure the data collection and avoid loss of follow-up, a member of research team will phone patients at 3 months and will also contact GPs at 9 months to insure closing of the follow-up.

*Quality control* will be provided by an independent GP and a hospital internist not aware of the current study. They will both review 20% of the cases, randomly

selected, to insure correct management of patients and validity of the data collected before analysis. Both reviewing and follow up should certify as surely as possible and without any invasive procedure the correct diagnosis and management of patients' complaint.

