## Suivi à 3 et 9 mois

Questionnaire rempli par : infirmière de recherche (analyse intermédiaire à **3 mois**)   
 médecin (terme du suivi à **9 mois**)

No patient :	No médecin :	Date :
--------------	--------------	--------

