### **Hospitalisations en lien avec la douleur thoracique durant la période de suivi :**

oui  / non

*Si oui*, durée : \_\_\_\_ jour(s)

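### The 3-month harm look relies on telephone interviews with reachable patients and a form with no death item, so it can understate harm

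*Protocol*

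**What the plan says.** **Purpose of the look.** Section 8.2: "Intermediate analysis is done at 3 months after patients index visit to display any unexpected effect of the CPR". An unfavourable effect on patients stops the study at once, and 3.4 lists the same ground among the stopping rules. No other look for harm during the trial is described.

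**Source of its data.** Section 3.1 has research staff who "will get in touch with every agreeing patient at three months (intermediate analysis". Section 7.2: "Questionnaires for intermediate analysis at 3 months will be filled in by research team during a telephonic interview". Section 9.1: "a member of research team will phone patients at 3 months". Section 6 also assigns the interim data to the research team. The Annex 3 form says of the 3-month version "Questionnaire rempli par : infirmière de recherche"; the physician completes the form only at 9 months.

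**Contact details.** Section 7.2: "Patients' details will be known only by their GP to insure maximal confidentiality". The GP keeps a list with each patient's name, code and phone number. For the research team, "only with patients' consent, mobile phone number is attached to identification code", with incomplete CRFs given as the purpose. The number is deleted after the interim (7.2, 11.4).

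**Content of the form.** Annex 3 asks about later consultations, tests, specialist referral, hospitalisation ("Hospitalisations en lien avec la douleur thoracique durant la période de suivi") and the final diagnosis. It has no item for death or vital status. Death is not a named endpoint in 3.2 or section 6 either.

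**Missing data.** Section 10.3 first tries to obtain the data from the GP or patient where feasible, then extrapolates, then excludes the patient.

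**The concern.** The trial sets out to show that tests can be spared without harming patients. The event that matters at the interim is a serious one, such as a missed coronary event, in the weeks after the index visit. An interview with the patient is the data source most sensitive to that event: a patient who has died cannot be interviewed, and one who is in hospital or very ill is less likely to answer. The form gives an informant other than the patient nowhere to enter a death.

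An interim that finds no unfavourable effect could then partly reflect who answered the telephone. Completing the data at 9 months does not help a decision taken on 3-month data.

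**Working it through.** No protocol figure is in dispute, so there is none to reproduce. The check has three steps. The first uses the text; the other two are illustrations on stated assumptions.

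**Step 1. What the described route captures at 3 months**

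| Patient's state at the call | Captured by the interview? | Other provision |
|---|---|---|
| Well, has given a number, answers | Yes | – |
| Admitted and discharged before the call, answers | Yes, through the hospitalisation item | – |
| Still in hospital or too ill to answer | No | 10.3, where feasible |
| Gave no number | No route described | 10.3, where feasible |
| Died | No, and no field on the form | 10.3, where feasible, but still no field |

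**Step 2. Share of events seen**

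Let r be the share of patients reached and h the event rate in unreached patients divided by that in reached patients. The protocol gives neither; both are assumptions.

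- Share of all events seen = r / (r + h(1 − r)).
- Event rate in reached patients divided by the true rate = 1 / (r + h(1 − r)).

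| h | r = 0.70: share seen | rate ratio | r = 0.50: share seen | rate ratio |
|---|---|---|---|---|
| 1 | 0.70 | 1.00 | 0.50 | 1.00 |
| 2 | 0.7/1.3 = 0.54 | 1/1.3 = 0.77 | 0.5/1.5 = 0.33 | 1/1.5 = 0.67 |
| 3 | 0.7/1.6 = 0.44 | 1/1.6 = 0.63 | 0.5/2.0 = 0.25 | 1/2.0 = 0.50 |

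At h = 1 the interim loses precision only. Bias appears when h exceeds 1, that is, when reach depends on the outcome.

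**Step 3. Effect on a difference between arms**

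Assumptions: true 3-month risk of death or serious event 2% in one arm and 3% in the other; 80% of event-free patients reached; the same reach in both arms; all 150 clusters of 50 per arm past 3 months; the coefficient of variation of 0.2 from section 10.1; two-sided 5% level.

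- Observed rate = p·e / (p·e + (1 − p)·n), where p is the true risk, e the reach in patients with an event and n the reach in the others.
- Example, e = 0.5: 0.02 × 0.5 / (0.010 + 0.98 × 0.8) = 0.010/0.794 = 1.26%, and 0.03 × 0.5 / (0.015 + 0.97 × 0.8) = 0.015/0.791 = 1.90%.
- Power = Φ(|a − b| / √(V/149) − 1.96), with V = a(1 − a)/m + b(1 − b)/m + 0.2²(a² + b²), where a and b are the observed rates and m = 50(0.98n + 0.02e) is the number reached per cluster.

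| Reach in patients with event / others | Observed rates | Difference | Power |
|---|---|---|---|
| 100% / 100% | 2.00% vs 3.00% | 1.00 point | 97% |
| 80% / 80% | 2.00% vs 3.00% | 1.00 point | 93% |
| 50% / 80% | 1.26% vs 1.90% | 0.64 point | 78% |
| 25% / 80% | 0.63% vs 0.96% | 0.32 point | 50% |
| 0% / 80% | 0 vs 0 | 0 | nothing seen |

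The last row is the case of death when interview data stand alone. Differences are taken before rounding.

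**The case against.** Several stronger readings are tempting, and the documents do not support them.

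- **That admitted patients as a group are lost.** Annex 3 asks about hospitalisation over the follow-up period, so anyone discharged and reached is counted. Only those still in hospital or too ill at the call are at risk.
- **That the interim is expressly limited to patients with a mobile number.** This is an inference. Section 7.2 ties the number to incomplete CRFs, 9.1 says without restriction that patients are phoned, and 3.1 does not define who is agreeing. The inference is plausible, because no other number is said to reach the research team and the number is kept until the interim. The patient information form (Annex 4) is not among the pages shown, so what patients agree to cannot be checked.
- **That unreached patients are dropped by default, and no death can ever become known.** Section 10.3 puts contact with the GP or patient first, and 3.1 has staff check that forms are complete. Both soften the problem. They do not remove it: contact depends on feasibility, no 3-month GP report is set, a contacted GP finds no death field, and exclusion is the last resort.
- **That the whole trial is affected.** GPs send index-visit CRFs for every patient, including tests and hospital referral at that visit, and GPs complete the 9-month follow-up. The exposure is to new events between the index visit and month 3, except that the missing death item also affects the 9-month form.
- **That the rule's sensitivity in section 5 shows how many events would be missed.** It describes how the score classifies patients, not how completely the interim records outcomes.

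It is also fair to say that the choice of patients for the interim analysis could be settled in a statistical analysis plan. The data source, the contact route and the form are fixed in this protocol, and a later plan cannot recover data that were not collected.

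**Conclusion.** The concern holds in this limited form. As written, the only look that can stop the trial for harm takes its new outcome data from patients well enough and reachable enough to be interviewed, on a form that cannot record a death, with GP back-up left to feasibility. It can understate harm in both arms and shrink a true difference.

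The mechanism rests on the text; the size does not. With twice the event rate in unreached patients, 54% of events are seen at 70% reach and 33% at 50%. In the arm comparison, a true 1.0-point excess shows as 0.64 or 0.32 point when 50% or 25% of patients with events are reached, and power falls from 97% with complete data to 78% or 50%. All reach and event rates here are assumptions. Equal reach in both arms is one too; if reach differed by arm, the comparison could be biased in either direction.

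The change should be made before enrolment, since the missing information cannot be rebuilt in time for the interim.

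**What to change.** 1. **Annex 3:** add a vital-status line (alive, or died with date and cause). It serves the 3- and 9-month uses alike.
2. **Sections 3.1, 7.2 and 10.3:** for every patient not interviewed at 3 months who has not withdrawn, require the GP to return vital status and hospitalisation under the patient code. For these two items this replaces the feasibility proviso and the fallback to exclusion.
3. **Sections 3.1, 7.2, 9.1 and 11.4:** reconcile who is phoned at 3 months, on which number and for which purpose, and match the consent wording.
4. **Interim report:** give 3-month ascertainment and data source (interview or GP) by arm.

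**Cost.** The GP already holds each patient's name, code and phone number and already sends coded forms, so confidentiality is kept and no extra staff are needed. The burden is one short form per unreached patient: if 30% are unreached (assumption), 0.30 × 50 = 15 per GP, or 0.30 × 15,000 = 4,500 in all. The interim would also mix nurse interviews with reports from GPs who know their arm. For objective items such as death and admission that drawback is limited, and reporting the source by arm makes it visible.
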